### **9.8 Modification of Study Agent(s)/Intervention(s) for a Participant**

Metronidazole in both treatment doses is the CDC recommended treatment for TV. The study will treat participants at baseline only. There will be no need for modification of study agents unless the participant is unable to complete a dose. Clinical protocols will be followed in case of severe reaction to MTZ.

### **9.8.1 Dose / Schedule Modifications for a Participant**

If the participant is unable to complete the dose of MTZ, she will be referred to her clinical provider for alternative treatment.

## **9.9 Halting Rules for the Protocol**

Since the study is taking place at public clinics, the investigators are physicians at the clinics, the drug intervention is recommended as treatment by the CDC, and the investigators have extensive experience, it is expected that SAEs will be minimal. If, however, during the course of the study, the number of side effects exceeds what is considered normal, the DSMB will recommend whether to continue without modification, continue with specified modification, discontinue one or more arms of the study, discontinue enrollment at one or more clinical sites or halt or modify the study until more information is available. If a major change is recommended, the DSMB will report this directly to the NIH Program Officer who will contact the PI and collectively make a determination on how to proceed. All DSMB recommendations and proposed changes to the protocol will be reported to the IRB. All adverse events will be reported to medical provider responsible for the participant and followed clinically to assure that the participant experiences the minimal amount of sequelae possible. Unexpected adverse events are reported to the participating institutions per their respective protocols.

## **9.10 Stopping Rules for an Individual Participant/Cohort**

Criteria for Discontinuation of Study Agent(s)/Intervention(s):

-if they are randomized to an arm and are unable to tolerate the dose the study agent will be discontinued.

Criteria for Withdrawal of a Participant:

-if they become incarcerated and are unable to attend follow up visits

-if any clinical adverse event, laboratory abnormality, concurrent illness, other medical condition or situation occurs such that continued participation in the study would not be in the best interest of the participant.

-if a woman is found to be pregnant after consent but prior to randomization

-if a woman is found to be ineligible after consent but prior to randomization

-if a participant initial TV positive wet prep result is not confirmed by either InPouch culture or TV NAAT test from her enrollment visit

Version: 11.0

Version date: 1/2/17

## **9.11 Premature Withdrawal of a Participant**

Voluntary withdrawal is always an option for participants without affecting their clinical care. Women may choose to withdraw from the study at any time. If they choose to withdraw the data that has been previously collected will be included in the analyses.

## **9.12 Replacement of a Participant Who Discontinues Study Treatment**

There is no plan in the protocol to replace women who discontinue the study. Enrollment will continue up until 2 months prior to the study end date.

# **10. Clinical Monitoring Structure**

## **10.1 Site Monitoring Plan**

The Principal Investigator and Tulane study staff under the direction and supervision of the PI, will conduct regular site monitoring to ensure human subject protection and that study procedures are being conducted as per protocol and Manual of Procedures as outlined in section 12.0. For the first 4 months of enrollment, weekly conference calls will be held with investigators and study personnel at sites to ensure start up activities are following protocol, any questions can be answered, and clinic flow and specific clinical issues can be addressed. The PI and Program Manager are available at any time via email or cell phone to address any urgent issues. Quarterly site visits will be conducted by the PI, or her designee. At these visits, at least 10% of study charts will be pulled and reviewed, all consent forms will be reviewed and consent procedures will be discussed. There will also be a systematic review of enrollment statistics (i.e., number of eligible patients, refusal log, ineligibility log). Weekly data transfer to the research office at Tulane University will allow the program manager to review data collected for any errors or discrepancies and report back to sites to resolve any inconsistencies.

Women will be systematically asked if they experienced any of the common side effects on the TOC CRF.

## **10.2 Safety Monitoring Plan**

The safety of the subjects is paramount. AE reports are monitored on an ongoing basis by the Principal Investigator at monthly meetings and by the DSMB. All SAEs are reviewed by the site and Lead PI (or designee) within 2 working days of receipt. Both AEs and SAEs are reported to the IRB according to each institution's regulations including the Tulane IRB. The DSMB reviews these at their bi-annual meetings. Events will be reported to the FDA in accordance with 21CFR312.32 guidelines.

Version: 11.0

Version date: 1/2/17

### **10.2.1 Safety Review Plan by the DSMB / SMC**

The DSMB will be responsible for monitoring all aspects of the study, including those that require access to blinded data, and will follow the procedures detailed in the DSMB charter (see appendix). A brief description of the DSMB activities is as follows.

The “convening authority” for the DSMB is NIH-NIAID. The DSMB will consist of three experts who are not otherwise affiliated with the study. The DSMB will meet semiannually and may meet more frequently if requested by members of the DSMB. These meetings will consist of three sessions: Open Session, Closed Session, and Closed Executive Session. The Data Coordinating Center (DCC) representative will be responsible for preparing and presenting up-to-date statistical reports on the progress of the study at these meetings. These reports will include data on recruitment, randomization, adherence, adverse drug responses as well as statistical tests and special analyses requested by the DSMB. The Open Sessions will be attended by DSMB members, a FDA representative, a DCC representative, the principal investigator and members of the study team as needed. All voting will occur during the Closed Executive Session, which is only attended by DSMB members.

During the active recruitment phase, the DSMB will monitor the progress of recruitment and the random allocation of participants to the various treatment arms and may recommend modifications in (or termination of) the trial if the study design goals are not being met. The DSMB may recommend discontinuation of any of the treatment arms for safety reason or a very low probability of successfully addressing the study hypotheses within a feasible time frame, because of inadequate recruitment, compliance, drug response, effect size of outcome, etc. All votes will be decided by a simple majority. The NIAID will make the final decision on whether or not to accept the DSMB's recommendation to discontinue any component of the study.

The approval of the DSMB will also be required for any significant changes in the protocol recommended during the course of the study.

## **11. STATISTICAL CONSIDERATIONS**

### **11.1 Overview and Study Objectives**

The overall goal of this project is to determine the influence of index treatment and host factors on repeat TV infections among HIV-negative women in two specific objectives: 1) To determine if the multi-dose (alternate) MTZ is superior to single dose (recommended) for the treatment of TV among HIV-negative women. 2) To determine if altered vaginal flora (measured by Nugent's score) interferes with the MTZ treatment of TV for the single dose but not the multi-dose.

Version: 11.0

Version date: 1/2/17

## **11.2 Study Population**

English speaking, HIV negative women, who are not pregnant or breastfeeding, and are of the age of majority, who attend a clinical exam at 4 public clinics and are found to be positive for *Trichomonas vaginalis*.

## **11.3 Description of the Analyses**

The TV positive rate will be compared between the two arms for superiority. Additional analyses will be conducted to compare the rates stratified by BV status.

## **11.4 Measures to Minimize Bias**

### **Enrollment/ Randomization/ Masking Procedures**

After eligibility is assessed, informed consent is obtained and the woman has completed the ACASI survey and self-swab collection, she will be randomized to treatment arm. A blocked randomization scheme will be used to avoid “runs” in the randomization process. Each site will have its own blocked randomization scheme. Pre-numbered, sealed envelopes will be selected sequentially and opened for each participant who will then be enrolled in the indicated treatment arm. Because we are conducting a phase III trial and behaviors associated with the interventions are important, we will not attempt to make the single dose mimic a 7-day dose by supplementing with placebo. The trial will, therefore, be un-blinded. There will be no replacement of participants who discontinue early. Enrollment will continue through two months prior to study end.

Study personnel will know which arm the participant was randomized to. This information will not be disclosed to laboratory personnel. The Program Manager will periodically ensure that all participants were randomized to the correct treatment arm as indicated in the randomization scheme. Any discrepancies will be immediately discussed with investigators to prevent further error.

## **11.5 Appropriate Methods and Timing for Analyzing Outcome Measures.**

The primary outcome measure is TV infection. All women will be TV positive at baseline and will be screened for TV using InPouch culture and NAAT at follow up visits. Binary (TV positive or TV negative)

Key secondary outcomes are:

Version: 11.0

Version date: 1/2/17

BV which will be measured by self-collected vaginal swabs and Gram stain screening at all visits. Categorical (Scores of 7 -10 are considered to indicate BV). This measure will add information about the primary outcome measure by indicating whether BV affects TV repeat infections.

Re-exposure, which will be self-report by the participant for each partner. This data will be collected on the behavioral survey at follow up visits. Binary (partner treated and /or no sexual exposure prior to screening vs. partner not treated and sexual exposure prior to screening, This measure will allow us to adjust for the confounding effects of sexual exposure/re-exposure.

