Study Duration	Participants will be enrolled in the study for the time it takes to complete their follow up visits (no more than 21 weeks). Accrual for the study will be 30 months in duration. Participants will be asked for permission to store their samples for future research and for investigators to use their data for secondary data analyses.
Study Agent/Intervention Description	Metronidazole 2g single oral dose under direct observation and Metronidazole 500 mg oral dose BID for 7 days with the first dose given under direct observation
Primary Objective	To examine the influence of two factors on repeat infections with TV among HIV negative women: dosing and the presence of bacterial vaginosis (BV):  We will test two hypotheses: H1: Women receiving multi-day MTZ will be less likely to test TV positive at TOC compared to women who receive the single dose MTZ.  H2: This effect (H1) will only be observed among women who have BV (Nugent score $\geq 7$ ).
Secondary Objectives	To determine the proportion of infections at follow up that are attributable to treatment failure or sexual re-exposure.
Exploratory Objectives	Examination of the rate and factors associated with adherence to medication, knowledge/belief/factors associated with partner treatment, sexual exposure and the nature of the sexual act and sexual partner, and condom use will be possible using the ACASI survey data. These factors will be assessed by arm to determine if any confounding occurred and if so, these analyses will be adjusted for these factors. These data will also help inform future translational research.
Endpoints	Repeat infection with Trichomonas vaginalis (TV) at 4 weeks (TOC) as measured by InPouch culture or NAAT.

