#### **3.2 Secondary Objectives**

To determine more precisely the origin of a TOC positive result using the results of the genotyping and the sexual histories and to determine if most of the infections are treatment failure, re-exposure, sexual exposure to a new partner or organism lack of susceptibility to MTZ.

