TV Genotyping methods - Until recently, genotyping of *T. vaginalis* was limited by the crudeness of the genotyping techniques, e.g. RAPDs and RFLPs. These methods are highly sensitive to contaminating DNA or to slight variations in assay conditions, which influence their ability to accurately characterize *T. vaginalis* isolates. A recently developed panel of 21 *T. vaginalis*-specific microsatellites now provides a sensitive, reproducible, highly discerning set of genetic markers to accurately determine isolate-specific haplotypes and mixed genotype infections. Because of the high polymorphism of these markers and the number of loci that can be assayed, minor variations in haplotypes can be detected, allowing for high-resolution discrimination between related strains. [name] laboratory at NYU will genotype baseline and repeat infection specimens from all patients testing positive for TV at follow-up (~40 per year, ~120 total over 3 yrs). Frozen stabilates will be sent to NYU overnight and shipments will follow all standard regulations for shipment of Category B biological substances. Both isolates from each individual will be genotyped at 11 MS loci as described with minor modifications. Briefly, microsatellite-specific NAAT reactions will be performed for each locus using fluorescently labeled primers, and fragment length polymorphisms at the loci will be measured

Version: 11.0

Version date: 1/2/17

by capillary electrophoresis on an ABI 3130xl sequencer and scored using GeneMapper 4.0.

The haplotypes determined for the baseline and repeat infection will be compared to make inferences about the origin of reinfection. In addition, ~120 non-repeat infections (~40 each year) will also be genotyped to identify local population genetic characteristics and address the issue of confounding population structure.

NAAT swabs will be placed in a GenProbe vaginal collection tube and stored at 2-30°C. Swabs will be couriered daily from the clinic to the clinical laboratories and shipped at least monthly to the LSUHSC or UAB laboratory. Shipment will follow all Category B shipping restrictions. Upon arrival, DNA isolation will be performed using published methods and nucleic acid diagnostic results will be returned within one week.

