Study staff will process the specimens: for Gram stain, the swab will be carefully rolled by study staff over a predefined area of a glass slide, air dried, and stored in a slide cover; for FMS, the swab will be placed in a tube with preservative; for InPouch, the swab will be placed in the culture medium; for NAAT, the swab will be placed in the GenProbe tube. The specimens will be labeled with study identification numbers and dates of collection.

She will then be randomized to treatment arm (Single dose or 7 day dose). A blocked randomization scheme will be used to avoid "runs" in the randomization process. Pre-numbered, sealed envelopes will be selected sequentially and opened for each participant who will then be enrolled in the indicated arm.

If a woman is randomized into the single oral dose MTZ arm, she will be given the 2 g dose of MTZ and asked to ingest it under direct observation. If a woman is randomized into the 7 day oral dose MTZ arm, she will be given the 500 mg BID for 7 days and asked to ingest the first dose under direct observation.

All participants will receive the same counseling: to refrain from unprotected sexual intercourse until 1 week after they and their partner(s) complete the medication, to refrain from alcohol consumption while taking the medication and for 24 hours after completion; MTZ-related adverse events will be discussed including rash, dizziness, headache, diarrhea, nausea, vomiting, fatigue, upset stomach, dark red-brown urine, and change in taste sensation (metallic taste) or dry mouth. It will also be explained that MTZ can cause urine to darken in color but that this effect is not harmful. Participants in the 7-day arm will be given additional counseling on the importance of taking all doses of the medication.

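### The re-exposure variable in section 11.5 ignores whether sex with a treated partner came before his treatment, so some re-exposed women are coded as not re-exposed and may be read as treatment failures

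*Combined protocol and SAP*

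**What the plan says.** Section 11.5 lists re-exposure among the key secondary outcomes. It is measured per partner by self-report ("Re-exposure, which will be self-report by the participant for each partner") and has two levels: "partner treated and /or no sexual exposure prior to screening vs. partner not treated and sexual exposure prior to screening". Its stated purpose is adjustment: "This measure will allow us to adjust for the confounding effects of sexual exposure/re-exposure". Section 11.13 also compares sexual re-exposure between arms and brings unbalanced confounders into the model.

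The Protocol Summary gives the secondary objective as "To determine the proportion of infections at follow up that are attributable to treatment failure or sexual re-exposure". Section 3.2 bases this on evidence about the "origin of a TOC positive result using the results of the genotyping and the sexual histories" and names several possible origins: "to determine if most of the infections are treatment failure, re-exposure, sexual exposure to a new partner". Sections 4.2.2 and 11.13 send the classification to the Figure 4 algorithm and plan to use treatment failure as a refined outcome for H1 and H2.

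On genotyping, section 7.2.2.2 says: "The haplotypes determined for the baseline and repeat infection will be compared to make inferences about the origin of reinfection". On behaviour, the counselling in section 8.2 tells women "to refrain from unprotected sexual intercourse until 1 week after they and their partner(s) complete the medication".

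**The concern.** The only time reference in the 11.5 rule is the TV test at follow-up. Nothing places sex before or after the partner's treatment. Take a woman who has unprotected sex with her infected partner in week 1, and whose partner takes medication in week 3. She has been re-exposed, yet the rule codes her as not re-exposed because he was treated. The counselling in 8.2 shows that the protocol itself regards the period before the partner's treatment has taken effect as one of risk.

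Two things are at stake. First, re-exposure is a key secondary outcome and adjustment variable, and a misclassified covariate adjusts incompletely. Second, the secondary objective has to separate persistence of the original infection from re-infection, and sexual history carries much of that distinction. If the same binary is used there, the timing error would move re-infections into the treatment-failure class. Added to both arms in similar absolute numbers, such infections would pull the odds ratio for the refined outcome towards 1, although the risk difference would be unchanged.

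**Working it through.** The plan has no figure of its own on this point, so the main check is logical.

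**Step 1. Truth table of the 11.5 rule (one partner).** Not re-exposed = treated OR no sex. Re-exposed = not treated AND sex.

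| Partner treated | Sex before the follow-up test | Code under 11.5 |
|---|---|---|
| Yes | Yes | Not re-exposed |
| Yes | No | Not re-exposed |
| No | Yes | Re-exposed |
| No | No | Not re-exposed |

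The two levels are complements, so every partner falls in one of them and the rule leaves no room for judgement.

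**Step 2. Split the first row by order.** Treated and sex only after the point named in 8.2: *not re-exposed* is reasonable. Treated but unprotected sex before that point: *not re-exposed* is wrong by the protocol's own counselling. The rule gives both the same code. There is time for this sequence, since section 8.3 allows the test-of-cure (TOC) visit 3-12 weeks after baseline in the single-dose arm and 4-13 weeks in the 7-day arm.

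**Step 3. Can genotype repair it?** A different haplotype at TOC points away from persistence. A matching haplotype does not separate persistence from re-infection by the original partner, who can carry the baseline strain. In addition, 7.2.2.2 describes preparing genotyping specimens from positive InPouch cultures, while the endpoint (4.2.1) is culture or NAAT. For a woman positive by NAAT only, the text describes no TOC isolate to type. In both situations sexual history has to carry the distinction.

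**Step 4. Illustration of size.** This assumes that Figure 4 uses the binary and sends same-strain, not-re-exposed positives to treatment failure. Inputs:
- Starting share of treatment-failure labels: 22/24 = 91.7%, from the earlier cohort in 2.1.4, where labels were assigned from sexual histories. It is a starting value only.
- Repeat infections: about 120, the genotyping forecast in 7.2.2.2. That gives 120 x 22/24 = 110 labels.
- q = share of those labels that are really same-strain re-infections from a partner treated late. **q is an assumption; the documents give no value.**

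Mislabelled = 110 x q. True share = (22/24) x (1 - q).

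| q | Mislabelled of 110 | True treatment-failure share |
|---|---|---|
| 0% | 0 | 91.7% |
| 5% | 5.5 | 87.1% |
| 10% | 11 | 82.5% |
| 20% | 22 | 73.3% |
| 30% | 33 | 64.2% |

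The 11.7 rates imply more infections: 1332/2 = 666 evaluable per arm, and 666 x 0.162 + 666 x 0.107 = 107.9 + 71.3 = about 179. Labels would be 179 x 22/24 = 164.1, and q of 10%, 20% and 30% would mislabel about 16, 33 and 49. The shares in the last column do not change.

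**The case against.** The strongest reply is that the damage to the secondary objective is not shown. A reader might infer that same-strain re-infections *are* counted as treatment failures. The documents do not support that. Origin is assigned by Figure 4, which is not readable in the text reviewed and whose absence is no fault of the plan. No passage says that the 11.5 binary feeds it, the stated use of the binary is confounder adjustment, and the sexual histories named in 3.2 may hold more detail. This stands, and the consequence can be put only as a risk.

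Four other inferences also go too far:
- *That any woman with a treated partner is coded as unexposed.* The variable is recorded per partner. A woman with one treated partner and another who was untreated and exposed need not be coded so. The text gives no rule for combining partners.
- *That the error runs only towards treatment failure.* The timing error does, but the binary also ignores condoms, so protected sex with an untreated partner is coded as re-exposure. The net direction is unknown.
- *That new partners and condom use are left out of the plan.* Section 3.2 names new partners as an origin, and 11.13 plans to examine condom use and the nature of the partner by arm. They are absent only from this binary.
- *That the primary result is biased.* The primary endpoint (4.2.1) is any positive test at TOC and does not use the variable. Only adjustment under 11.13 could bring it into the primary model.

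What the reply does not remove is the definition itself. It is a stated rule that gives the wrong code to an identifiable group, not a detail left for later.

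**Conclusion.** The concern holds for the definition. Section 11.5 codes a treated partner as no re-exposure whatever the order of sex and treatment, so women whose exposed partners were all eventually treated can be misclassified in a key secondary outcome and adjustment variable. Genotype cannot correct this where the original partner carries the baseline strain.

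The effect on the secondary objective and on the refined H1/H2 outcome is conditional on Figure 4 using this binary. The size is unknown. The range of 11 to 33 mislabelled among about 120 rests on an assumed q of 10% to 30% and on a 22/24 starting share borrowed from an earlier cohort. The primary endpoint and the sample size are not affected. The change should be made, because the attribution of repeat infections depends on exposure history and the remedy is cheap.

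**What to change.** Replace the binary in 11.5 with a per-partner rule based on order in time:

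- **Re-exposed:** between enrolment and TOC the woman had unprotected sex with a baseline partner who was not treated, or with a treated baseline partner before the post-treatment point already used in the 8.2 counselling. That point serves here only to classify data.
- **New partner:** a separate code, since 3.2 lists it as a separate origin.
- **Possibly re-exposed:** sex with a partner whose treatment status is unknown. Report the attribution twice, with this group placed either way.
- **Combining partners:** class a woman as re-exposed if any partner meets the rule.
- **Figure 4:** state that the algorithm uses this variable, and how it classes a same-strain positive in each category.

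Collect the order of sex and partner treatment in the follow-up ACASI if it is not already asked. The instrument is not among the documents, so this may need no new items. The cost is analysis-plan wording and at most a few partner-level questions. The downside is recall over up to 13 weeks of events the woman may not know exactly, such as when her partner took his medication, and so a larger *possible* class.
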